9.2.3. Adverse Event or Concomitant Medications Dates or Times

For AEs with missing or partially missing start date/time, the following imputation rules will be applied for the determination of treatment-emergent status:

If an AE has a partial onset date and time, the collected or imputed start and stop dates and times will be used to determine treatment-emergence (e.g., an AE with stop date and time before the start date and time of study treatment is not treatment-emergent).

- If the year is unknown, then the date will be assigned the date and time of first dose of study treatment.
- If the year is known to be different from the year of the first dose, then missing month and day will be imputed as the first month and first day of the month.
- If the year is known to be the year of the first dose,
 - a) If the month is unknown or is the same as the month of the first dose, then the missing month and day will be imputed by the month and day of the first dose.
 - b) If the month is known to be different from the month of the first dose, then the missing day is imputed as 01 (first day of the month).
- If the time is unknown, then:
 - a) If the date (day, month, and year) matches the date of the administration of study drug, then the time of the study treatment will be used to impute the missing time.
 - b) Otherwise, '00:00' will be assigned.

For medications with missing or partially missing dates, Section 9.2.3 provides rules for the determination of prior or concomitant status.

9.2.4. Adverse Event Severity or Relationship to Study Drug

If severity of an AE is not reported, then for tables of AEs by severity, the event will be classified as 'Severe' and will be footnoted for the table to indicate this imputation. If relationship to study drug is not reported for an AE, then for tables of study-drug related AEs, the event will be assigned the relationship of 'definite'. Tables presenting related AEs will include all AEs with relationships of 'possible', 'probable' or 'definite' as assessed by the investigator.

9.2.5. Time to Event

For calculating time to an event when only the hour is reported, the minutes will be set to zero. The censoring method is described in Sections 6.3.1 and 6.3.2 when the onset time or the offset time of sensory or motor block is not captured.

9.3. Subject Disposition

Subject disposition summaries will include the number (and %) of subjects by treatment group.

- Screened,
 - Screen failure
 - Enrolled (ie, randomized)
- Randomized

- Randomized not treated
- Randomized treated
- In the Safety analysis set
- In the Efficacy analysis set
- In the Pharmacokinetic analysis set
- In the Pharmacodynamics analysis set
- Protocol
 - Enrolled under each amendment
- Completed the study as planned
- Discontinued from the study
 - Reasons for discontinuation from the study

Percentages will be reported for the screen failures and enrolled using the number of subjects screened as the denominator; other percentages will use the number of subjects randomized and treated as denominator. All data will be presented as randomized, although analysis for Safety set (see Section 9.8) will be based on the actual treatment patients received.

9.4. Description of Demographics and Baseline Characteristics

9.4.1. Demographics

The summary of demographic data will present:

- Age (years) descriptive statistics
- Sex n (%)
- Ethnicity n (%)
- Race -n (%)

Age is calculated at the date the subject signed the informed consent form. It is presented as the number of years rounding down to the nearest integer.

The demographic summary will present the data for each treatment group. Summaries will be provided for each (efficacy, safety, PK and PD) analysis set separately.

9.4.2. Baseline Characteristics

The summary of baseline characteristic data will present:

- American Society of Anesthesiologists (ASA) Classification n (%)
- Height (cm)
- Weight (kg)
- Body Mass Index (BMI) (kg/m²)
- Average and Worst pain intensity scores on the numeric rating scale (NRS) in the last 30 days

• Pain Catastrophizing Scale Total Score

Weight in pounds will be converted to kilograms using the conversion factor of 2.2046 pounds to 1 kilogram. Height in inches will be converted to centimeters using the conversion factor of 2.54 centimeters to 1 inch.

The Pain Catastrophizing Scale Total Score is the summation of the 13 questions.

Baseline characteristics summaries will present the data for each treatment group. Summaries will be provided for each (efficacy, safety, PK and PD) analysis set separately.

Descriptive statistics (n, mean, SD, median, minimum and maximum) will be provided for continuous variables. The number and percent of subjects will be tabulated for the categorical variables.

9.4.3. Medical and Surgical History

Subject medical and surgical history will be provided in a by treatment group and subject data listing.

9.4.4. Surgery Characteristics

Surgery characteristics including duration of surgery will be summarized using descriptive statistics. Summaries will be provided for each (efficacy and safety) analysis set.

Duration of surgery is calculated as the difference between the end of surgery and start of surgery times and reported in hours.

9.4.5. Intraoperative, Prior, and Concomitant Medications

All medications will be coded using the World Health Organization Drug Dictionary Enhanced (WHO Drug Dictionary Global September 2020 C3 Format) and will be classified according to the anatomical therapeutic chemical classification term (ATC) and preferred term (PT).

Intraoperative medications are defined as medications given as part of the surgical procedure. These may include anesthesia, opioids or other medications collected on the Intraoperative Medication CRF Page.

Prior and Concomitant medications are medications collected on the Prior/Concomitant Medication eCRF page. Prior medications are defined as medications with a stop date and time prior to the start of study drug administration. Concomitant medications are defined as medications taken after the start of study drug administration (i.e., started prior to the start of study drug administration and continued after or started after the start of study drug administration).

For the determination of the prior and concomitant status, these rules will be followed for incomplete dates.

• If the medication stop date is partially missing,

- If the year and month indicate the stop date is before study drug administration, it is Prior medication.
- Otherwise, it is concomitant medication.
- If the medication stop date is completely missing, it is concomitant medication.

All medications will be summarized separately by category using n (%) of subjects for each treatment group and across treatment groups by ATC3 term and PT for the safety analysis set. Subjects may have more than one medication per ATC3 and PT. At each level of subject summarization, a subject will be counted once if one or more medications are reported by the same subject at that level.

All medications will be included in the data listing.

9.4.6. Measurements of Treatment Compliance

Study drug is administered by the site personnel; therefore, compliance is assumed.

9.5. Efficacy Analysis

For Primary and Secondary Efficacy Analyses, descriptive statistics that are appropriate for the efficacy variable will also be shown by surgical type, but no statistical analyses will be performed within a surgery type. All efficacy analyses will be performed using the Efficacy analysis set.

Unless specified otherwise, all confidence interval will be 2-sided with 95% confidence. All statistical comparison will be 2-sided at alpha=0.05 level. The leading statistical comparison is between EXPAREL and 0.25% bupivacaine HCl for the primary and first two secondary endpoints and between EXPAREL and EXPAREL admixed with 0.25% bupivacaine HCl for the third and fourth secondary endpoints, though all 3 pairwise comparisons (EXPAREL vs 0.25% bupivacaine HCl, EXPAREL vs EXPAREL admixed with 0.25% bupivacaine HCl, and EXPAREL admixed with 0.25% bupivacaine HCl, and EXPAREL admixed with 0.25% bupivacaine HCl, will be presented.

To control for the overall Type-I error rate for the multiple comparisons, the statistical tests will be conducted in the hierarchical order as follows. See also Section 8.1 for detail.

- 1. Primary endpoint: EXPAREL vs 0.25% bupivacaine HCl
- 2. First secondary endpoint: EXPAREL vs 0.25% bupivacaine HCl
- 3. Second secondary endpoint: EXPAREL vs 0.25% bupivacaine HCl
- 4. Third secondary endpoint: EXPAREL vs EXPAREL admixed with 0.25% bupivacaine HCl

5. Fourth secondary endpoint: EXPAREL vs EXPAREL admixed with 0.25% bupivacaine HCl

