15.6.3. Efficacy Analyses

All efficacy analyses will be based on the efficacy analysis set and will be analyzed according to the randomized treatment. The primary efficacy endpoint will be additionally analyzed by stratifying by surgery on the efficacy analysis set as a sensitivity analysis.

For continuous measures of efficacy, summary statistics (n, mean, median, standard deviation, minimum, and maximum) will be shown by treatment group. For categorical measures of efficacy, number and percentage of subjects in each category will be shown by treatment group. For time to

event measures of efficacy, medians and Kaplan-Meier estimates will be shown by treatment group.

Baseline is defined as the last non-missing assessment of a given assessment prior to first dose of trial drug unless otherwise specified.

All assessments will be presented in by-subject data listings.

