	POD 7	168h	±3h	х	х		
	POD 6	144h	±3h	х			
	S OOJ	120h	±3h	Х	Х		
		96h	±3h	Х	Х		
		84h	±2h	Х	Х		
_	04)	72h	±2h	Х	Х		
tration	4 (POI	60h	±2h	х	х		
dminis	ve Day	48h	±1h	х	х		
Drug A	operati	30h	±1h	х	Х		
study]	o Post-	24h	±1h	х	Х		
Post-	tration t	12h	±30m	Х	Х		
	Adminis	8h	±30m	Х	Х		
	ly Drug .	2h	±30m	х	Х		
	y of Stud	1h	±15m	Х	Х		
	Da	45m	45m ±5m X		Х		
		30m ±5m		Х	х		
		15m	±5m		х		
		Up to 15 mins	before blocks	Х	Х		
		Time Window		Collect PK blood sample; Record date and time of blood sample	Assess and record sensory and motor function ^{b,c}		

Table 2: Pharmacokinetic and Pharmacodynamic Assessment Schedule (Cohort 1 bunionectomy subjects only)

Abbreviations: h=hour; m=minute; PK=pharmacokinetic

a. All timepoints are from end of block administration.

- Once offset of sensory and motor block are determined (in two consecutive evaluations), no subsequent assessments will be conducted. Sensory and motor are assessed independently م
- When subject is in surgery, no sensory or motor block assessments be conducted.

5. **DEFINITIONS**

Start and End of Block

See Sections 6.3.1 and 6.3.2 for onset and offset of sensory block and motor block, respectively.

Study Day

Study Day is calculated as the date of event minus the date of end of study drug administration plus one (1), if the date of event is on or after the date of end of study drug administration. If the date of event is before the end of study drug administration, study day is the date of event minus the date of study drug administration.

Time 0

For PK, PD, and safety evaluation, Time 0 is defined as the date and time of the end of the study drug administration. For NRS pain collection and opioid consumption, Time 0 is defined as the date and time of the end of the surgery.

Baseline

Baseline is defined as the last available measurement prior to start of study drug administration.

Surgical Type

It is expected this study will enroll patients for bunionectomy, 1st metatarsophalangeal fusion, specific forefoot surgeries, midfoot fusion, hindfoot fusion, and total ankle arthroplasty. Due to overwhelmingly large number of bunionectomy patients enrolled as of this date, patients will be subgrouped into bunionectomy and non-bunionectomy for the purpose of by-subgroup summaries.

Treatment-Emergent Adverse Events (TEAEs)

TEAEs are those with onset date and time on or after the start date and time of study drug administration.

Beginning of Surgery

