9.5.1. Primary Efficacy Endpoint

The primary efficacy endpoint is AUC of the NRS pain intensity scores from 0 to 96 hours postoperation using Efficacy Analysis Set. The NRS pain intensity score is collected from the assessment "How much pain are you experiencing right now?" The worst and average daily pain scores are not included in the AUC calculation.

AUC curve is derived using the trapezoidal rule (see formula below) on the pain scores adjusted for opioid pain medication using the observed and imputed values (see Section 9.2.2). AUC will start with the first pain assessment obtained after surgery (arrival at PACU) and use all subsequent pain assessments up to 96 hours post-surgery. Pain scores collected prior to the opioid medication administration or unscheduled are also included in the AUC calculation. Exact assessment time will be used in deriving AUC.

$$AUC = \left\{ \sum_{i=2}^{n} (p_i + p_{(i-1)})(t_i - t_{(i-1)}) \right\} / 2$$

Where p_i is the NRS pain score at time *i* and t_i is the time, in hours, from end of surgery. Note t_i is pain score collected upon PACU arrival. It is the first time NRS score is collected.

In calculating AUC_{0-96} , if the exact 96-hour pain score is not collected, it will be interpolated using the two nearest before and after data points. If the last 96-hour assessment is before 96.0 hours, then the exact 96-hour pain score for the AUC calculation will use this last observation carried forward.

 $AUC_{0.96}$ for pain intensity from 0 to 96 hours will be summarized by treatment group, by surgery type and overall.

Tests for the superiority of treatment effect of EXPAREL versus 0.25% bupivacaine HCl will be based on the following null hypotheses and alternative hypotheses using the Efficacy analysis set and multiple imputation method:

H_o: EXPAREL is not different from 0.25% bupivacaine HCl with respect to AUC for pain intensity

HA: EXPAREL is superior to 0.25% bupivacaine HCl with respect to AUC for pain intensity

A two-sided hypothesis test will be performed at 5% level of significance comparing EXPAREL and 0.25% bupivacaine HCl as follows:

If the upper bound of the 2-sided 95% confidence interval for the least square (LS) means for the difference of AUC₀₋₉₆ (EXPAREL) – AUC₀₋₉₆ (0.25% bupivacaine HCl) is ≥0, then superiority of EXPAREL to 0.25% bupivacaine HCl is not achieved.

• If the upper bound is <0 then declare that the superiority of EXPAREL to 0.25% bupivacaine HCl is achieved.

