9.5.3. Subgroup Analysis for the Primary and First Secondary Efficacy Endpoints

The analysis of the primary and the first secondary endpoints will be repeated for select subgroups such as

- Age (<45, and \geq 45),
- Sex
- Race (White and Non-White),
- BMI (<25, 25 to <30, and \ge 30+ kg/m²)
- Height (<165 cm, and \geq 165 cm)
- Site
- Surgical Type

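### SAP 9.5 rules out statistical analysis within a surgery type but 9.5.3 calls for it, and the separate within-level tests in 9.5.3 can suggest differing effects where there are none

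*SAP*

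**What the plan says.** - **SAP 9.5** gives descriptive statistics by surgical type for primary and secondary efficacy, "but no statistical analyses will be performed within a surgery type". It also states "All statistical comparison will be 2-sided at alpha=0.05 level", and it sets a five-step testing hierarchy that contains no subgroup.
- **SAP 9.5.1** says the AUC "will be summarized by treatment group, by surgery type and overall". It declares superiority when the upper 95% confidence limit for EXPAREL minus bupivacaine HCl is below 0.
- **SAP 9.5.3** says: "The analysis of the primary and the first secondary endpoints will be repeated for select subgroups such as". The list is age, sex, race, BMI, height, site and "Surgical Type".
- **SAP Section 5** (Definitions, surgical type) gives two levels: "patients will be subgrouped into bunionectomy and non-bunionectomy for the purpose of by-subgroup summaries". The reason stated is "Due to overwhelmingly large number of bunionectomy patients enrolled as of this date".
- **SAP 9.2.2** shows the code for the primary model, with treatment, site, age and height. The output includes the LS mean difference, its 95% CI and a p-value.
- **Protocol 15.6.3** adds: "The primary efficacy endpoint will be additionally analyzed by stratifying by surgery on the efficacy analysis set as a sensitivity analysis".

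**The concern.** A programmer cannot follow both rules. If 9.5 governs, surgery type gets descriptive statistics only. If 9.5.3 governs, the primary and first secondary analyses are re-run among bunionectomy subjects and again among the rest, with CIs and p-values. If this stays open until the data are unblinded, the choice can be made with the results in view.

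The question matters because all of Cohort 1 is bunionectomy while the objectives are framed for lower extremity surgeries. A reader will ask whether the effect extends beyond bunionectomy. Two separate tests answer that badly: a significant result in the large level beside a non-significant one in the small level looks like a difference in effect, even when the true effects are equal.

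**Working it through.** **1. Can the passages be reconciled?**
- The qualifier at the head of the second paragraph of 9.5 (unless specified otherwise) governs the confidence intervals, not the bar on analysis within a surgery type.
- Section 5 speaks of summaries and 9.5.1 says summarized. Both lean towards description, but neither overrides 9.5.3.
- Reading 9.5 as covering only the six individual procedures does not help, because the bunionectomy level is itself one procedure.
- The list in 9.5.3 is introduced by such as, so it is illustrative, but surgical type is named and the instruction is that the analysis will be repeated.
- The protocol's surgery-stratified sensitivity analysis is one analysis of the whole efficacy set, not a test inside each type.

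The conflict stands.

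**2. Inputs.** Difference δ = 150, SD σ = 170, two-sided 0.05, 40 per arm (SAP 10). Cohort 1 is about 60 bunionectomy subjects randomized 1:1:1 (SAP 4), so bunionectomy has at least about 20 per arm and non-bunionectomy at most about 20 per arm. Actual counts are not given, so the splits below are assumptions.

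**3. The plan's own figure.** SE = σ√(2/n) = 170 × √(2/40) = 38.0, so δ/SE = 3.95. Two-sample t-test power (noncentral t) is 97.4%, or 97.6% by the normal approximation. The plan's statement of at least 90% is therefore true.

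**4. Separate tests, same true effect of 150 in both types.** Power P(n) comes from the noncentral t with noncentrality 150/(170√(2/n)) and 2n − 2 degrees of freedom. The two levels contain different subjects, so

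P(discordant) = P_b(1 − P_n) + P_n(1 − P_b),

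where b is bunionectomy and n is non-bunionectomy. The last column is 1.96 × 170√(2/n) for non-bunionectomy.

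| Per arm, b/n | P_b | P_n | P(discordant) | 95% CI half-width, non-bunionectomy |
|---|---|---|---|---|
| 20/20 | 0.776 | 0.776 | 0.35 | 105 |
| 30/10 | 0.919 | 0.463 | 0.53 | 149 |
| 34/6 | 0.948 | 0.283 | 0.70 | 192 |
| 36/4 | 0.958 | 0.184 | 0.79 | 236 |

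Example, 30/10: 0.919 × 0.537 + 0.463 × 0.081 = 0.494 + 0.038 = 0.53.

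**5. Sensitivity to the variance estimate.** The SAP model may pool the variance over three arms, which gives more degrees of freedom. Treating the SD as known is the limit of that gain. The powers are then 0.797/0.797, 0.927/0.505, 0.953/0.333 and 0.963/0.238, and the same formula gives 0.32, 0.50, 0.65 and 0.74. The conclusion does not change.

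**6. What an interaction model would give.** SE = 170√(2/n_b + 2/n_n), half-width = 1.96 × SE, and power for an interaction of 150 = Φ(150/SE − 1.96).

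| Per arm, b/n | SE | 95% CI half-width | Power, interaction = 150 |
|---|---|---|---|
| 20/20 | 76.0 | 149 | 0.51 |
| 30/10 | 87.8 | 172 | 0.40 |
| 34/6 | 106.5 | 209 | 0.29 |
| 36/4 | 126.7 | 248 | 0.22 |

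Even an interaction as large as the whole planned effect would often be missed. The gain is one contrast with an honest interval, not a powered test.

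**7. Site.** Site is a factor in the model in 9.2.2. Inside a single site that term is constant and cannot be estimated, so the analysis cannot be repeated literally there. Age and height are also both covariates and subgroup factors, but they still vary within their levels.

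**The case against.** The strongest reply is that this is a one-line wording conflict with limited consequences. Much of that stands. The descriptive result by surgery type is fixed, the subgroups lie outside the hierarchy, and no text available plans a claim from a subgroup. The sentence in 9.5 also agrees with Section 5 and 9.5.1, and it covers secondary endpoints that 9.5.3 does not reach, so deleting it would remove a useful restriction. The interaction test is itself weak.

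Three stronger readings are tempting, but the documents do not support them:

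- A reader might infer that the non-bunionectomy test would probably fail even with an identical effect. Power is 78% at 20 per arm, 65% at 15 and 46% at 10, so this holds only at about 10 per arm or fewer. Section 5 points to imbalance but gives no count. Small does not describe the bunionectomy level at all.
- A reader might infer a serious false-positive problem. The six factors other than site have 2 + 2 + 2 + 3 + 2 + 2 = 13 levels. Over two endpoints that is 26 tests, and 1 − 0.95^26 = 0.74. That figure assumes independence, whereas every factor divides the same subjects again and both endpoints come from them. It also says nothing about the alpha of the trial's confirmatory tests.
- A reader might infer that the SAP contains no interaction model anywhere. That can be said only of 9.5.3 and the code in 9.2.2. Later sections refer to 9.5.1 for the model specification and sensitivity analyses, and the closing part of 9.5.1 is missing from the available text.

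The reply does not remove the contradiction, or the risk of misreading if 9.5.3 is followed.

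**Conclusion.** The conflict between 9.5 and 9.5.3 is certain from the wording. It leaves open one thing: whether an inferential result by surgery type is produced for the primary and first secondary endpoints. If 9.5.3 is followed as written, equal true effects would give discordant significance about 35% of the time at the most even split the plan allows, and 53% to 79% of the time at 30/10 to 36/4 per arm.

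These figures rest on the planning difference and SD holding in both types, the assumed splits, and a simple two-group comparison without covariates or imputation. They apply to the AUC only, since the documents give no planning values for opioid consumption. This is a problem of interpretation and reporting that should be corrected. It does not threaten the primary conclusion.

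**What to change.** 1. **SAP 9.5:** keep the sentence and add an explicit exception for the exploratory analyses in 9.5.3. The minimum alternative is to remove surgical type from the 9.5.3 list, which leaves surgery type purely descriptive.
2. **SAP 9.5.3:** replace the repeated within-level analyses by one model per factor on the whole Efficacy set, adding the factor and treatment-by-factor to the primary model. Report the EXPAREL minus bupivacaine HCl difference with 95% CI for each level, and the interaction estimate with its CI. For opioid consumption, do the same on the log scale already planned.
3. **Labelling:** call these results exploratory, make no significance claim within a level, and note that the interaction test has low power (about 22% to 51% for an interaction of 150 under the splits above).
4. **Site:** drop the site covariate when estimating within a site, or show site results only as a descriptive plot.

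The change should be made before unblinding. It costs a few lines of SAP text and simple programming. The downside is that within-subgroup p-values are no longer reported.
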